- Provide a thorough characterization of the patient population that presents with segmental bone defects that warrant surgical reconstruction (specific aim 1);
- Establish defect characteristics among the study subjects treated with the Masquelet versus the CTMC procedure (part of specific aim 2);
- Collect and analyze the distribution of patients within specific study arms (Option A vs Option B) (part of specific aim 3);
- Establish the cost or preoperative and surgical management of the study subjects;
- Provide an analysis of patients with segmental bone deficiency who did not meet study eligibility criteria;
 - Establish the extent of patient compliance with immediate and early postoperative regimen.

3. Study Follow-up Period (18 months)

This period encompasses the timeframe of the last 18 months, i.e. from termination of enrollment to study completion. This period's primary objective is to successfully complete follow-up of all enrolled patients. During this period the following study tasks are expected to be accomplished:

- Continuing postoperative data collection;
- Analysis of data collection process (consistency, redundancy, dropout rate);
- Tentative statistical analysis of the collected data;
- Establish costs of subject follow-up incurred;
- Itemize all resource expenditure for total treatment costs assessment.

Milestone #4: Follow-up completion of 30 study subjects

4. Study Post Completion Period (2-4 months)

This period encompasses the timeframe after the study has been terminated. The research efforts in this period include:

- Thorough analysis of all pre-, intra-, and postoperative variables collected in the study to accomplish the specific study aims 2, 3 and 4.
- Assessment of the safety and efficacy of the CTMC defect reconstructive technique
- Establishing the clinical indications and treatment recommendation for CTMC the based upon the treatment outcome;
- Assessment of the total resource expenditure related to the CTMC reconstruction technique (in accordance with the graft option type) and comparison with the standard defect reconstruction modalities (study specific aim 5);
- Data presentation at international/national research meetings.
- Manuscript preparation and submission to a high-impact-factor peer-reviewed journal.

Milestone #5: Data presentation in research forums

Milestone #6: Manuscript publication

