NCT 02015390

**The Comparative Efficacy of the Masquelet versus Titanium Mesh Cage
Reconstruction Techniques for the Treatment of Large Long Bone Deficiencies**

PI: [name], PhD
[name]

The University of Texas Medical Branch; Galveston, TX

Jun 22, 2020

STATISTICAL PLAN AND DATA ANALYSIS:

Statistical Methodology

Descriptive statistics will be used to analyze the collected data specifically to:

- characterize the patient with segmental bone deficiency;
- estimate the proportion of healing with/without complications;
- cross-compare the recorded variables.

Paired Student t-test will be used to test the effects of the Masquelet versus the CTMC defect reconstruction on the outcome measures.

Analysis of covariance (ANCOVA) will be used for pair-wise comparison within the two treatment arms (graft Option A vs. Option B).

A mixed model for repeated measures will be conducted to evaluate:

- the effect of the Masquelet versus CTMC defect reconstruction on the outcome measures, adjusting for patient demographics and clinical characteristics;
- the effect of the specific defect characteristics (etiology, size, location, adjacent soft tissue involvement, etc) on the treatment outcome;
- the possible interaction effects between treatment and defect characteristics.

Multiple models will be used in case the proposed sample size would not have enough power to produce an accurate predictive model which accounts for all possible morbidities and interactions. Simple models using modern penalty function techniques (lasso, elastic net, boosted trees, etc.) to control model complexity should provide a useful initial predictive tool for each clinical and quality of life outcome.

Both receiver operating curve (ROC) analysis and clinical judgment will be used in determining the optimal clinical indications and timing for defect reconstitution with the definitive defect reconstruction using the Masquelet versus the CTMC technique.

Sample Size Justification

Based on the data from the PIs' preliminary clinical series of 20 patients, it can be assumed that 75% of patients with segmental bone defects reconstructed with the CTMC technique will heal without complications. In the present study we propose to enroll and follow-up 30 patients throughout 4 years of the clinical trial duration.

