This sample size of 30 is largely determined by clinical feasibility. For the sample size 30, a two-sided 95% confidence interval for a single proportion using the large sample normal approximation will extend 0.134 from the observed proportion for an expected proportion of 0.75.

Our past experience with a prospectively investigating 20 patients with traumatic segmental defects presented to our institution (single site) within 3.5-year period suggests that the 30 patients to be enrolled in the proposed study within the anticipated time frame is very feasible considering broader inclusion criteria and multi-site study location.

Data Analysis

Prospectively collecting pertinent pre-, intra-, and postoperative study variables will establish a database of patients with segmental bone defects reconstructed with CTMC in combination with bone graft or bone graft substitute. A series of multivariate models will be constructed to model sizeable complex interactions between the patient, defect etiology and characteristics, process of care variables and surgical outcomes. Specific analyses will be performed to address the following questions:

- What are the characteristics of the patients who present with segmental bone deficiency warranting surgical reconstruction that achieve superior functional and quality of life outcomes when treated with the Masquelet versus the CTMC technique?
- What is the nature of a segmental bone defect and its related variables that determine superior outcomes after the Masquelet versus the CTMC reconstruction?
- What are the aspects of pre-, intra-, and postoperative care that differ for patients who:
 - A) achieve poor outcomes;
 - B) sustain treatment related complications;
 - C) incur resource usage well in excess of the average?

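### ROC analysis is named for setting the indications for Masquelet versus CTMC but is not tied to the planned treatment interaction, so a purely prognostic factor can pass for an indication and a true modifier can be missed

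*SAP*

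**What the plan says.** SAP, Statistical Methodology, with the same text in the protocol section of that name: "receiver operating curve (ROC) analysis and clinical judgment will be used in determining the optimal clinical indications and timing for defect reconstitution", for Masquelet versus CTMC. No marker, outcome or cut-off rule is given, nor whether curves are pooled, drawn by arm or compared between arms.

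Earlier in that section the mixed model is to cover prognosis ("the effect of the specific defect characteristics (etiology, size, location, adjacent soft tissue involvement, etc) on the treatment outcome") and, separately, effect modification ("the possible interaction effects between treatment and defect characteristics"). That interaction is limited to defect characteristics and is not mentioned in the ROC sentence.

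SAP, Data Analysis, asks comparative questions. One concerns the patients "that achieve superior functional and quality of life outcomes when treated with the Masquelet versus the CTMC technique". Another is: "What is the nature of a segmental bone defect and its related variables that determine superior outcomes after the Masquelet versus the CTMC reconstruction". It also plans this: "A series of multivariate models will be constructed to model sizeable complex interactions between the patient, defect etiology and characteristics". Treatment arm is not named among the interacting terms.

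Indications are a stated product of the trial. The protocol's Study Post Completion Period lists "Establishing the clinical indications and treatment recommendation for CTMC the based upon the treatment outcome".

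**The concern.** An indication for one technique over the other is a claim about the difference between arms: the difference must change with the characteristic. The matching null hypothesis is that there is no treatment-by-characteristic interaction. An ordinary ROC curve addresses something else, namely whether the characteristic discriminates between good and poor outcomes, with an AUC of 0.5 meaning that it does not.

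The two can part company in both directions. A factor that worsens healing equally under both techniques yields a good AUC and a cut-point, yet gives no reason to prefer either technique. A factor that reverses which technique is better can leave the pooled AUC at 0.5. Finding the curve significant in one arm and not in the other does not settle the matter, because that is not a test of the difference between arms.

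At stake is the advice on who should receive which technique. The only statistical method named for that step does not, in its ordinary form, contrast the arms.

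**Working it through.** The plan states no figure for the ROC or interaction analyses, so there is none to reproduce. From the documents: 30 patients, 15 per arm (protocol, Treatment Arm Randomization), and an expected 0.75 healed without complications, stated for CTMC (SAP, Sample Size Justification) and applied here to both arms. All marker effects below are assumptions.

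**1. Exact example with a binary marker, 50% prevalence.** AUC = ½ × (1 + P(marker present | healed) − P(marker present | not healed)).

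- Prognostic only: healing 0.90 with the marker and 0.60 without, in both arms. Overall healing = 0.5 × 0.90 + 0.5 × 0.60 = 0.75. P(present | healed) = 0.45/0.75 = 0.60; P(present | not healed) = 0.05/0.25 = 0.20. AUC = ½ × (1 + 0.60 − 0.20) = 0.70, pooled and in each arm. The difference between techniques is 0 at both marker levels.
- Crossover: Masquelet 0.60 with the marker and 0.90 without; CTMC 0.90 and 0.60. Pooled healing is 0.75 at both levels, so the pooled AUC is 0.50. The CTMC minus Masquelet difference is +0.30 with the marker and −0.30 without, an interaction of 0.60. The by-arm AUCs are 0.30 and 0.70.

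**2. Simulation at the trial's size.** Standard normal marker; score = slope × marker + normal error with SD 1; score cut so that about 75% have a good outcome; 3,000 to 4,000 trials per scenario; nominal 5%. ROC is the Mann-Whitney test of AUC = 0.5. The interaction test is the marker-by-arm t-test (26 df) in a linear model of the binary outcome. The AUC comparison is an unpaired DeLong test between arms; trials with fewer than 2 patients in an outcome class in either arm (about 15%) count as non-rejection. Ranges show the spread between repeated runs.

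| Slopes (two arms) | Pooled ROC | ROC significant in exactly one arm | Interaction, binary outcome | By-arm AUCs compared |
|---|---|---|---|---|
| 0.5, 0.5 (AUC about 0.71) | 40–41% | 27–30% | about 5% | 6.6% |
| 0.8, 0.8 (AUC about 0.80) | 72–74% | 44–46% | about 5% | 4.0% |
| 1.0, 1.0 (AUC about 0.85) | 85–87% | 49–50% | about 5% | 3.5% |
| −0.8, +0.8 | 4% | 42% | 71% | 66% |

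In the first three rows there is no differential benefit, so every rejection read as an indication is a false one. The exactly-one-arm reading is nearly as frequent there (up to 50%) as under the crossover (42%), so it barely separates the two situations.

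**3. A different data model.** With a logistic outcome and slope 1.2 in both arms, mean AUC is 0.78, ROC is significant in 65% of trials and the interaction in 4%. With slopes −1.2 and +1.2, the pooled AUC averages 0.50, ROC is significant in 4% and the interaction in 63%.

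**4. What the interaction can deliver with 30 patients.** For a binary marker at 50% there are about 7.5 patients per cell. On a continuous outcome in SD units, SE = √(4/7.5) = 0.73. The interaction detectable with 80% power is (1.960 + 0.842) × 0.73 = 2.05 SD. Power is about 28% for 1 SD and 54% for 1.5 SD.

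**The case against.** The best defence is that the ROC analysis is unspecified, and that a pooled AUC tested against 0.5 is an analysis the plan never describes. The sentence ends by naming both techniques, so curves drawn and compared by technique would fit it. It also follows directly on the predictive models, so ROC may be meant to assess those. A formal comparison of by-arm AUCs does contrast the arms: it rejects in 66% of trials under the crossover, close to the 71% for the interaction, and in 33% against 30% under a milder one (−0.4, +0.4). This stands. ROC as such is not ruled out; the ordinary pooled curve and the one-arm-only reading are.

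A reader might infer that indications are to be set by ROC alone and that effect modification goes untested. The documents do not support that. Clinical judgment is named alongside ROC, a treatment-by-defect interaction is planned, and nothing says that ROC overrides it. What remains is that the plan does not say which result decides, that judgment is no test of differential benefit, and that no explicit treatment interaction covers patient characteristics although a question about them is asked.

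A reader might also take the crossover contrast as 4% against 96%. That larger figure comes from giving the interaction test the continuous score and ROC only the dichotomised one. On the same binary outcome it is 71%.

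Finally, the protocol (Resources Expenditure and Cost-Effectiveness Analysis) makes the comparison of outcome between arms the primary determination. The indications step is therefore not the trial's main conclusion.

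**Conclusion.** The concern holds in a limited form. The plan names ROC, with clinical judgment, for deciding when one technique is preferable to the other, and leaves that step unconnected to the interaction that fits the question. Under the ordinary uses of ROC, a prognostic factor can be taken for an indication, and a factor that truly changes the choice can be missed; the documents do not show that either will happen.

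The size is about 40% to 87% rejection by pooled ROC where there is no differential benefit, against about 5% for the interaction, and about 4% against 71% under a full crossover. These rates rest on assumed slopes, a single normally distributed marker and about 75% good outcomes in both arms. An exact sign reversal is the extreme case that forces the pooled AUC to 0.5. The mismatch between statistic and question does not depend on those values, as the binary example shows. The plan should be changed, and the change is one of wording.

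**What to change.** In Statistical Methodology of both the SAP and the protocol, replace the ROC sentence so that it says:

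- Any statement that a patient or defect favours one technique rests on the treatment-by-characteristic interaction, reported as the difference between arms with its 95% CI across values of the characteristic.
- The interaction covers a short, prespecified list of characteristics. To the defect characteristics already planned, add the few candidate patient characteristics needed for the first question under Data Analysis.
- These results are exploratory.
- ROC analysis describes prognosis and is not used to choose between techniques. If it is kept for that purpose, the only admissible form is a formal comparison of AUCs between arms, with marker and outcome stated beforehand.

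No further patients or data are needed, and most of the model is already planned. The cost lies in what can be claimed: with 15 per arm, intervals will be wide and 80% power is reached only for an interaction of about 2 SD, so few indications, perhaps none, will be supported.

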NCT 02015390

**The Comparative Efficacy of the Masquelet versus Titanium Mesh Cage
Reconstruction Techniques for the Treatment of Large Long Bone Deficiencies**

PI: [name], PhD
[name]

The University of Texas Medical Branch; Galveston, TX

Jun 22, 2020

THE STUDY PROTOCOL

The proposed study is a single-center, prospective, two-arm, randomized clinical trial. The study is conducted and coordinated by the University of Texas Medical Branch (UTMB) and its affiliated John Sealy Hospital; Galveston, TX as a study site. Patients who present to these hospitals with a traumatic segmental bone loss (high-energy trauma, gunshot injury) or a medical condition (infection, nonunion, tumor) which requires iatrogenic segmental bone resection will be enrolled into the study after inclusion/exclusion criteria have been met and signed informed consent obtained. Routine patient management (standard of care) will be performed prior to the Masquelet or the cylindrical titanium mesh cage (CTMC) reconstruction in accordance with the patient's bone defect characteristics and overall health status. Post enrollment, the study subjects will be randomized into either the Masquelet (Arm I) or the CTMC defect treatment technique (Arm II). All aspects of pre-, intra-, and postoperative patient and defect management will strictly adhere to the IRB-approved study research protocol. Within each study arm, two distinct options of bone graft will be available for use in combination with the Masquelet or the CTMC defect reconstruction, and they include: autogenous RIAharvested bone graft (Option A) obtained from reaming of either the intramedullary femoral or tibial canal, or fresh-frozen cancellous allograft in combination with demineralized bone matrix (Option B). The decision on graft option is made by the patient following an in-depth review by a treating physician (study PI).

STUDY DESIGN:

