Based on the data from the PIs' preliminary clinical series of 20 patients, it can be assumed that 75% of patients with segmental bone defects reconstructed with the CTMC technique will heal without complications. In the present study we propose to enroll and follow-up on 30 patients throughout 4 years of the clinical trial duration. This sample size of 30 is largely determined by clinical feasibility. For the sample size 30, a two-sided 95% confidence interval for a single proportion using the large sample normal approximation will extend 0.134 from the observed proportion for an expected proportion of 0.75.

Our past experience with prospectively investigating 20 patients with traumatic segmental defects presented to our institution (single site) within 2.5-year period suggests that the 30 patients to be enrolled in the proposed study within the anticipated time frame is very feasible considering broader inclusion criteria.

Data Analysis

Prospectively collecting pertinent pre-, intra-, and postoperative study variables will establish a database of patients with segmental bone defects reconstructed with CTMC in combination with bone graft or bone graft substitute. A series of multivariate models will be constructed to model sizeable complex interactions between the patient, defect etiology and characteristics, process of care variables and surgical outcomes. Specific analyses will be performed to address the following questions:

- What are the characteristics of the patients who present with segmental bone deficiency warranting surgical reconstruction that achieve superior functional and quality of life outcomes when treated with the Masquelet versus the CTMC technique?
- What is the nature of a segmental bone defect and its related variables that determine superior outcomes after the Masquelet versus the CTMC reconstruction?
- What are the aspects of pre-, intra-, and postoperative care that differ for patients who:
 - A) achieve poor outcomes;
 - B) sustain treatment related complications;
 - C) incur resource usage well in excess of the average?

Resources Expenditure and Cost-Effectiveness Analysis

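### The two supports for a sample size of 30 are faulty as written: the accrual history and site structure conflict between documents, and the 0.134 half-width belongs to n = 40

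*SAP*

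**What the plan says.** Neither document gives a power calculation. Both Sample Size Justification sections carry the same sentence on the origin of the number: "This sample size of 30 is largely determined by clinical feasibility". Two things then support it.

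- **Accrual history.** The SAP says that experience with 20 earlier patients with traumatic defects at one site "within 3.5-year period suggests that the 30 patients to be enrolled in the proposed study within the anticipated time frame is very feasible". The protocol refers to "20 patients with traumatic segmental defects presented to our institution (single site) within 2.5-year period". The surrounding sentence is otherwise nearly the same, and both documents are dated Jun 22, 2020.
- **Precision.** Both state that, with 30 patients and an expected proportion of 0.75, a two-sided 95% normal-approximation interval for a single proportion extends 0.134 either side. The 0.75 is the assumed rate of healing without complications under the cage (CTMC) technique.

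The reasons for expecting better accrual also differ. The protocol cites broader inclusion criteria only. The SAP calls the target "very feasible considering broader inclusion criteria and multi-site study location". The protocol opens with "The proposed study is a single-center, prospective, two-arm, randomized clinical trial" and repeats the single-center description in its data and safety monitoring plan (section III, Study Design). Plural wording about hospitals or sites remains in the protocol's opening paragraph, in Study Follow-up and in the preparatory period of Study Time Frame.

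The enrolment window appears only in the protocol's Study Time Frame: 30 patients in 32 months, then 18 months of follow-up, in a study described as lasting 4 years.

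**The concern.** When a sample size comes from a power calculation, an accrual history is background. Here it is the main argument for the number, so its inputs have to be right. One series cannot have taken both 2.5 and 3.5 years, so at least one document is wrong. The choice matters, because it decides whether accrual must rise by about two fifths or nearly double. The SAP also counts on a multi-site structure that the protocol's design statements do not describe.

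The only quantitative support besides accrual is the 0.134. If that is also wrong, a reader who accepts 30 as the feasible number is misled about what 30 patients will deliver.

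**Working it through.** **Precision, starting from the plan's own figure.** Inputs from Sample Size Justification: n = 30, p = 0.75, two-sided 95%, normal approximation. Half-width = 1.96 × √(p(1 − p)/n), with p(1 − p) = 0.1875.

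- n = 30: 1.96 × √(0.1875/30) = 0.155. The stated 0.134 is not reproduced.
- n = 40: 1.96 × √(0.1875/40) = 0.134. Solving for n gives 1.96² × 0.1875/0.134² = 40.1.
- Variants at n = 30 do not explain it: a 90% interval gives 0.130, and a continuity correction (adding 0.5/30) gives 0.172. At n = 30, ±0.134 has nominal confidence of about 91%.
- n = 15, the size of the CTMC arm under Treatment Arm Randomization: 1.96 × √(0.1875/15) = 0.219.

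The per-arm figure matters because the 75% is an assumption about CTMC patients. Only 15 of the 30 receive that technique, even with full enrolment.

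**Accrual.** Inputs: 20 past patients in 2.5 years (protocol) or 3.5 years (SAP); 30 patients in 32 months (protocol, Study Time Frame).

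| Quantity | Protocol, 2.5 years | SAP, 3.5 years |
|---|---|---|
| Past rate per month | 20/30 = 0.667 | 20/42 = 0.476 |
| Expected in 32 months at that rate | 0.667 × 32 = 21.3 | 0.476 × 32 = 15.2 |
| Multiple needed for 30 | 30/21.3 = 1.41 | 30/15.2 = 1.97 |
| Months to reach 30 at that rate | 30/0.667 = 45 | 30/0.476 = 63 |

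**Does another window rescue the claim?** The sample size text mentions only 4 years. Over all 48 months the protocol rate gives 32.0 and the SAP rate 22.9, so only the first reaches 30, and it leaves no time for the 18-month follow-up. If follow-up must fit inside the 4 years, 48 − 18 = 30 months remain for enrolment. Expected numbers are then 20.0 and 14.3, and the multiples needed are 1.5 and 2.1. The 32-month window is therefore the more favourable of the two that allow full follow-up.

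**Half-widths with no increase in accrual.** At 21 patients: 1.96 × √(0.1875/21) = 0.185. At 15 patients in total: 0.219. These are scenarios in which the past rate does not change. The second equals the CTMC-arm figure at full enrolment only because both have n = 15.

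**The case against.** The strongest reply is that neither document claims the past rate is enough. The earlier series was limited to traumatic defects, and the trial also admits nonunion, osteomyelitis and nonmalignant tumor. The protocol adds an active physician referral program (Human Subject Recruitment and Safety Procedures), further referral effort and advertising if accrual is slow (Study Time Frame), patient choice of graft partly to help enrolment (Study Design), and six-monthly meetings that can respond to enrolment problems (Course of Action). A 1.41-fold rise from such changes is not implausible. This stands. A reader might infer from 21 or 15 that 30 is unattainable, or take 0.185 and 0.219 as the expected precision of the whole trial. The documents support neither inference, because both assume no increase at all. What remains is that no document attaches a size to any of these offsets, and the increase needed depends on which accrual period is true.

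A second tempting reading is that the SAP's multi-site argument is simply false. The protocol's explicit design statements favour a single center, and no second enrolling site is named, but its own plural wording means that it is not wholly consistent either. The documents show a conflict to be reconciled across both; removing one SAP phrase would leave the protocol's plurals in place.

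Finally, the half-width error is independent of the accrual conflict. That is true. The two belong together only because they are the two supports offered for the same number. Neither changes an estimand, a test or a decision rule.

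**Conclusion.** The point holds in this form: both supports for 30 are faulty as written.

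- The accrual history contradicts itself (2.5 against 3.5 years), as does the site structure on which the SAP relies. Reaching 30 in 32 months needs 1.41 or 1.97 times the past rate, an increase that neither document quantifies. The strong feasibility claim is unsupported, not disproved. The multiples rest on the 32-month window and make no allowance for refusal or ineligibility beyond what the past series already reflected.
- The 95% half-width of 0.134 is wrong on the plan's own formula and inputs. The value is 0.155 at n = 30, larger by a factor of 0.155/0.134 = 1.16. For the CTMC arm alone it is 0.219. This part needs no assumption beyond those the plan states.

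The documents do not show which accrual period is correct.

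**What to change.** 1. Verify the accrual period of the 20-patient series and give the same figure in both documents.
2. State one site structure throughout. If the trial is single-center, remove the multi-site argument from the SAP and the plural-site wording from the protocol's opening paragraph, Study Follow-up and Study Time Frame.
3. Replace the general statement of feasibility with the expected number in 32 months at the verified past rate, the multiple needed for 30 (1.41 or 1.97), and the measures expected to supply it, with a size for each where one can be given.
4. Replace 0.134 with 0.155 for n = 30 in both documents, and add 0.219 for the 15-patient CTMC arm.
5. If half-widths at lower enrolment are shown (0.185 at 21, 0.219 at 15 in total), label them as scenarios with no increase over past accrual.

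The cost is wording in two documents and one check of past records. No procedure or analysis changes. The downside is that stated feasibility and precision both look less favourable.
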